17.1 Case Report Form (CRF) Procedures

Data for this study will be captured in the EDC. The investigator or his/her designee is responsible for recording all data relating to the trial on the eCRFs in accordance with the site's contract with Gradalis. The investigator must verify that all data entries on the eCRFs are accurate and correct.

APPENDIX A

KARNOFSKY AND LANSKY PERFORMANCE SCALES

Karnofsky		Lansky		
Score	Description	Score	Description	
100%	No symptoms.	100%	fully active, normal	
90%	Able to carry on normal activity; minor signs or symptoms of disease.	90%	minor restrictions in strenuous physical activity	
80%	Able to carry on normal activity with effort; some signs or symptoms of disease.	80%	active, but tired more quickly	
70%	Cares for self, unable to carry on normal activity or do active work.	70%	greater restriction of play and less time spent in play activity	
60%	Requires occasional assistance but is able to care for most of own needs.	60%	up and around, but active play minimal; keeps busy by being involved in quieter activities	
50%	Requires considerable assistance and frequent medical care.	50%	lying around much of the day, but gets dressed; no active playing participates in all quiet play and activities	
40%	Disabled; requires special care and assistance.	40%	mainly in bed; participates in quiet activities	
30%	Severely disabled; hospitalization indicated, although death not imminent.	30%	bed-bound; needing assistance even for quiet play	
20%	Very ill; hospitalization necessary; active supportive treatment required.	20%	sleeping often; play entirely limited to very passive activities	
10%	Moribund, fatal processes progressing rapidly.	10%	doesn't play; does not get out of bed	
0	Patient expired.	0	unresponsive	

APPENDIX B

SCHEDULE OF ASSESSMENTS

Procedure	Prestudy / Surgery Pre- Screening	Protocol Screening	Day 1 of each Cycle ¹ (unless otherwise noted)	End of TX	Response Follow-Up (q 3mo±7 days) Until Progression
Informed consent	X	Х			
Medical History	X				
Physical Examination	X	Х	Х	Х	Х
Toxicity (adverse events)		from time of procurement	Х	Х	
Concomitant medications		Х	Х	Х	Х
Performance Status		Х	Х	Х	Х
Radiological Tumor Assessment (chest/abdomen/pelvis)		within 4 weeks (must be post- procurement)	every 6 weeks ± 7 days from Cycle 1	Within 45 days	х
CBC with differential	X ²	Х	Х	Х	Х
HIV testing, if applicable		Х			
Hepatitis testing, if applicable		Х			
Serum Chemistry	X ³	Х	Х	Х	Х
PBMC collection for Immune Function Analysis	≤ 1 week of tumor procurement	х	Cycles 2, 4, and 6 Day 1 prior to chemotherapy administration	х	3 months post EOT and q 6 months thereafter
Plasma collection for ctDNA	≤ 1 week of tumor procurement	х	Cycles 2, 3, 4, and 6 Day 1 prior to chemotherapy administration	х	
Pregnancy Test (if applicable)		х			
Tissue Procurement	Х				
Vigil administration depending on randomization			Day 15 q 21±3 days 4		
Injection Site Assessment			Day 16 only (may be conducted at home) ⁵		
Temozolomide			Days 1 – 5, q21 days		
Irinotecan			Days 1 – 5, q21 days		
Survival Status	X				Long Term Follow Up ⁶
Immunohistochemistry		X ⁷			

¹ Subjects who are stable at the end of Cycle 4, with prior approval by the Sponsor may conduct evaluations on Day 15 of each cycle (1 Cycle = $21 \text{ days} \pm 3 \text{ days}$) (See Section 9.0).

² Obtain from medical records from standard preoperative hematology and chemistry panels.

³ Obtain from medical records from standard preoperative hematology and chemistry panels.

⁴ Cross-over subjects will receive Vigil on Day 1.

⁵ Cross-over subjects will have assessment on Day 2.

⁶ After progression, subjects will be contacted by phone quarterly for documentation of post study therapies and survival status.

⁷ These slides should correlate with tumor procured for vaccine manufacture.

REFERENCES

- (2016, September 28, 2016). "Ewing Sarcoma Treatment (PDQ®)–Health Professional Version." Retrieved 01/31/2017, from https://www.cancer.gov/types/bone/hp/ewing-treatment-pdq.
- Arvand, A. and C. T. Denny (2001). "Biology of EWS/ETS fusions in Ewing's family tumors." Oncogene 20(40): 5747-5754.

1.0 INTRODUCTION

This document describes the statistical methods and data presentations to be used in the summary and analysis of safety and efficacy data from Gradalis Protocol CL-PTL-130. Background information is provided for the overall study design and objectives. The reader is referred to the study protocol and case report forms (CRFs) for details of study conduct and data collection.

2.0 STUDY RATIONALE

The results from the Phase I Vigil trial show product safety (both short-term and long-term through 3+ years), confirm effective transgene expression (GMCSF) and RNAi [furin] silencing, and support the rationale of the immunotherapeutic triad, i.e., autologous tumor cell therapy with increased GMCSF expression and decreased TGFβ production shown to effectively modulate immunogenicity as evidenced by the correlation of IFNy-ELISPOT responsiveness with overall survival and the elicitation of the CD4+ mediated circulating antibody responses against CT47 in two of the Phase 1 Ewing's sarcoma patients. The preliminary evidence of safety, immune stimulation and clinical benefit from Vigil in patients with Ewing's sarcoma treated in the Phase I setting supports evaluation of this therapy in a larger and randomized study and at earlier stage of recurrence (first recurrence). A lower tumor burden is typically associated with greater delay in progression with other immunotherapies. Mathematical modeling supports the concept of better control of disease progression with the combined use of effective chemotherapy (e.g., temozolomide/irinotecan as second line treatment in Ewing's sarcoma) and immunotherapy (i.e., Vigil) in first relapse patient population (de Pillis, Gu et al. 2006). The utilization of the standard of care temozolomide/irinotecan regimen at investigator consensus defined dose and schedule appears to be minimally immunosuppressive and thus a reasonable option for combination with Vigil. Moreover, the temozolomide and irinotecan regimen at effective dose levels has low myelosuppressive toxicities (irinotecan 50mg/m²/dose and temozolomide 100mg/m²/dose) and may increase the tumor antigen release and surface exposure of calreticulin (part of the specific danger-signaling system) as well as reduce the frequency of CD4+ CD25+ regulatory T-cells (Kim, Kim et al. 2010). In addition, given that Ewing's sarcoma expression levels of type-1 associated chemokine ligands CXCL9, CXCL10, and CCL5 correlate with TIL expression chemokine receptors (CXCR3 and CCR5) (Berghuis, Santos et al. 2011) it is notable that temozolomide has been shown to enhance tumor matrix presentation of CXCL9 and CXCL10 in certain tumor models (Tan, Evrard et al. 2015). Temozolomide and irinotecan in combination have shown benign safety profiles without any Grade 3 treatment-related adverse events in seven combination treated Ewing's Sarcoma patients of Part 2 of CL-PTL-121. Furthermore, clinical antitumor activity was demonstrated in 4 of the 7 combination treated patients, all of whom had previously failed temozolomide and irinotecan, as evidenced by 2 partial responses, one histological CR (autopsy) and one prolonged SD currently near 1 year in duration. Thus, the combination of Vigil, irinotecan and temozolomide may not only increase anti-tumor responses but also prolong time to progression and improvement of guality of life in Ewing's sarcoma patients.

3.0 OBJECTIVES

3.1 Primary objective(s)

• To compare the progression free survival of subjects dosed with Vigil immunotherapy in combination with irinotecan and temozolomide vs. irinotecan and temozolomide.

3.2 Secondary objective(s)

- To determine and compare the overall survival of subjects with relapsed or refractory Ewing's sarcoma dosed with Vigil immunotherapy in combination with irinotecan and temozolomide.
- To determine the objective response rate (RECIST 1.1) of patients with metastatic Ewing's sarcoma refractory or intolerant to 1 prior line of systemic chemotherapy treated with Vigil immunotherapy or dosed with Vigil immunotherapy in combination with irinotecan and temozolomide.
- To determine the Vigil manufacturing success rate by gathering data from tumor tissue collection, Vigil construction, and test procedures.

4.0 END POINTS

4.1 **Primary Endpoint**

The primary endpoint of PFS is the time from randomization to progression according to RECIST version 1.1 or death. Incomplete data resulting from patients who terminate the study for reasons other than disease progression or death will be censored in time-to-event analyses on the last assessment date at which a RECIST 1.1 evaluation of disease status was made. The distributions of PFS in the two arms will be compared using a two-sided log-rank test.

4.2 Secondary Endpoint

The secondary endpoint of OS is defined as time from randomization to death or to the date of last follow-up. The date of last follow-up confirming survival will be used as the censoring date for subjects who are alive and/or do not have a known date of death. The analysis of OS will be conducted using the two-sided log-rank test. Kaplan-Meier OS curves will be displayed by treatment arm. Median OS and percent OS at fixed time points will be estimated.

The secondary endpoint of ORR will be analyzed using Pearson's chi-square test.

All secondary analyses will be conducted using two-sided tests at the alpha=0.05 level of significance.

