16.4.2 Secondary Efficacy Analyses

A fixed sequence testing procedure will be used to control the overall level of significance for the analysis of the secondary endpoints of OS and ORR. If the primary analysis of PFS is statistically significant (p<0.0476), then OS will be analyzed using a two-sided test at the alpha=0.0476 level of significance. In addition, if the analysis of OS is statistically significant (p<00476), then ORR will be analyzed using a two-sided test at the alpha=0.0476 level of significance. However, if an earlier analysis is not statistically significant, the remaining analyses will be exploratory rather than confirmatory.

The secondary endpoint of OS is defined as time from randomization to death or to the date of last follow-up. The date of last follow-up confirming survival will be used as the censoring date for subjects who are alive and/or do not have a known date of death. The analysis of OS will be conducted using the two-sided log-rank test. Kaplan-Meier OS curves will be displayed by treatment arm. Median OS and percent OS at fixed time points will be estimated.

The secondary endpoint of ORR will be analyzed using Pearson's chi-square test. Overall response rate (ORR) is defined as the proportion of patients who have a partial or complete response to therapy according to RECIST 1.1. ORR will be reviewed 6 months after treatment with Vigil.

The analyses of all other secondary endpoints will be conducted using two-sided tests at the alpha=0.05 level of significance.

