8.1.2 Secondary Efficacy Analyses

A fixed sequence testing procedure will be used to control the overall level of significance for the analysis of the secondary endpoints of OS and ORR. If the primary analysis of PFS is statistically significant (p<0.0476), then OS will be analyzed using a two-sided test at the alpha=0.0476 level of significance. In addition, if the analysis of OS is statistically significant (p<00476), then ORR will be analyzed using a two-sided test at the alpha=0.0476 level of significance. However, if an earlier analysis is not statistically significant, the remaining analyses will be exploratory rather than confirmatory.

The secondary endpoint of OS is defined as time from randomization to death or to the date of last follow-up. The date of last follow-up confirming survival will be used as the censoring date for subjects who are alive and/or do not have a known date of death. The analysis of OS will be conducted using the log rank test. Kaplan-Meier OS curves will be displayed by treatment arm. Median OS and percent OS at fixed time points will be estimated.

The secondary endpoint of ORR will be analyzed using Pearson's chi-square test. Overall response rate (ORR) is defined as the proportion of patients who have prolonged stable disease or a partial or complete response to therapy according to RECIST 1.1. ORR will be reviewed 6 months after treatment with Vigil.

The secondary analysis of all secondary endpoints will be conducted using two-sided tests at the alpha=0.05 level of significance.

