8.3 Interim Analysis

An interim analysis for efficacy, futility, and potential sample size re-estimation will be conducted by an independent data monitoring committee (IDMC) when 40 PFS events have been achieved (60% information fraction). Based on the Lan-DeMets method for group sequential trials using O'Brien-Fleming boundaries (Reboussin, DeMets et al. 2000), the levels of significance for the interim and final analyses are alpha=0.00762 and alpha=0.0476, respectively.

Based on the results of the interim analysis, the IDMC will make one of the following four recommendations to the sponsor:

- Terminate the study for efficacy (p<0.00762 at the interim analysis);
- Continue the study as planned;
- Increase the sample size to 120 events;
- Terminate the study for futility.

Provided that the IDMC does not recommend terminating the study early for efficacy, the conditional power of the planned final analysis at 67 events will be computed using the methodology of (Harrington 2001) (Jennison and Turnbull 2000), under the assumption that the observed hazard ratio at the interim analysis represents the true effect. In terms of the HR observed at the interim analysis, these rules can be translated (approximately) as follows:

- If the HR is less than 0.43, terminate for efficacy
- If the HR is in the range from 0.43 to 0.51, continue as planned.
- If the HR is in the range from 0.51 to 0.61 (i.e., conditional power in the range from 50% to 80%), increase the sample size to 120 events.
- If the HR is greater than 0.61 (i.e., conditional power less than 50%), terminate for futility.

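### Two SAP sentences put all secondary analyses at 0.05, against the SAP's own fixed sequence at 0.0476, so the rule that governs OS and ORR is unclear

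*SAP*

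**What the plan says.** SAP section 8.1.2 opens with a hierarchical rule: "A fixed sequence testing procedure will be used to control the overall level of significance for the analysis of the secondary endpoints of OS and" (the sentence then names ORR as the second endpoint). If PFS is significant at 0.0476, "then OS will be analyzed using a two-sided test at the alpha=0.0476 level of significance". If OS is then significant, "then ORR will be analyzed using a two-sided test at the alpha=0.0476 level of significance". A failed step has a stated consequence: "if an earlier analysis is not statistically significant, the remaining analyses will be exploratory rather than confirmatory".

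The same section closes with a different level: "The secondary analysis of all secondary endpoints will be conducted using two-sided tests at the alpha=0.05 level of significance".

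SAP section 4.2 defines OS and ORR as the secondary endpoints, mentions no gate on PFS, and ends: "All secondary analyses will be conducted using two-sided tests at the alpha=0.05 level of significance".

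Protocol section 16.4.2 has the same fixed sequence, but its closing sentence is narrower: "The analyses of all other secondary endpoints will be conducted using two-sided tests at the alpha=0.05 level of significance".

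The level 0.0476 comes from the group sequential design for PFS. SAP section 8.3 says that "the levels of significance for the interim and final analyses are alpha=0.00762 and alpha=0.0476, respectively".

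**The concern.** Neither 0.05 sentence in the SAP is limited to endpoints outside the sequence. Section 4.2 names only OS and ORR, so its sentence can apply to nothing else there. The one remaining secondary objective, in SAP 3.2 and protocol 4.2, is the Vigil manufacturing success rate, for which no comparison between arms is described. In practice, the 0.05 rule falls on the two endpoints that the sequence is meant to protect.

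Two kinds of result are affected:

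- **A p-value between 0.0476 and 0.05 for OS or ORR.** It is significant under the 0.05 sentences and not significant under the sequence.
- **A nominally significant OS or ORR result after an earlier step has failed.** Suppose PFS fails and OS gives p = 0.03. The sequence makes OS exploratory. Section 4.2, read alone, tests it at 0.05 and finds it significant.

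The SAP does not say which section prevails. Its introduction sends the reader to the protocol and case report forms for study conduct and data collection, not for testing rules. The trial is open label, which adds to the reasons for settling the rule before results are known.

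**Working it through.** **Inputs.** Interim and final two-sided levels 0.00762 and 0.0476, and information fraction 60% at 40 PFS events (SAP 8.3). Levels of 0.0476 and 0.05 for OS and ORR (SAP 4.2 and 8.1.2). The documents give no correlation between the OS and ORR test statistics, so a range is shown.

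**Step 1: is 0.0476 a derived level or a slip for 0.05?** Lan-DeMets spending of O'Brien-Fleming type, with 0.025 per side, spends per side at fraction t:

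2 × [1 − Φ(z₀.₉₈₇₅ / √t)]

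- At t = 0.60: 2.2414 / 0.7746 = 2.8936. The spend is 0.00381 per side, or 0.00762 two-sided.
- The final critical value c₂ solves 1 − P(|Z₁| < 2.668, |Z₂| < c₂) = 0.05, with correlation √0.60 = 0.7746. This gives c₂ = 1.981, a two-sided level of 0.0476.

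Both stated levels are reproduced. At the exact fraction 40/67 they would be 0.00744 and 0.0477. So 0.0476 is intended, and 0.05 is a different threshold. The gap is 0.05 − 0.0476 = 0.0024.

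**Step 2: fixed sequence at 0.0476.** A false claim requires rejection of the first true null hypothesis in the order PFS, OS, ORR. That hypothesis is tested at 0.0476, so the error at the final analysis is at most 0.0476. A simulation of 4 million draws (assumed correlation 0.3) gave 0.0475 to 0.0476 whether all three nulls were true, only OS and ORR, or only ORR.

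**Step 3: gates kept, OS and ORR tested at 0.05.** The same argument caps the error at about 0.05. The simulation gave 0.0477 with all nulls true, 0.0498 with OS and ORR null, and 0.0499 with only ORR null. If a look at 0.00762 is also taken at the interim, assuming 60% information for that endpoint too:

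1 − P(|Z₁| < 2.668, |Z₂| < 1.960) = 0.0523, correlation 0.7746

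The same formula with 0.0476 at the final analysis gives 0.0500. The plan does not say whether OS is tested at the PFS interim, so 0.0523 is conditional.

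**Step 4: 0.05 sentences read as ungated tests of OS and ORR.** Chance of at least one false claim when both nulls are true:

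| Assumed dependence of OS and ORR | Error |
|---|---|
| Independent: 1 − 0.95² | 0.0975 |
| Correlation 0.3 | 0.0951 |
| Correlation 0.5 | 0.0907 |
| Correlation 0.8 | 0.0781 |
| Upper bound, any dependence: 0.05 + 0.05 | 0.10 |

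**Summary of the readings**

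| Reading | Error for false claims |
|---|---|
| Fixed sequence at 0.0476 | at most 0.0476 at the final analysis |
| Gates kept, level 0.05 | about 0.050 (0.0523 with an interim look) |
| No gates, level 0.05 | 0.0975 if independent, at most 0.10 |

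**The case against.** The strongest reply is that control has not gone. The fixed sequence stands in SAP 8.1.2 and in protocol 16.4.2, with an express statement of what follows when a step fails. The 0.05 sentences give a level and say that tests are two-sided. They do not cancel the order of testing, and neither says that a result at 0.05 would be confirmatory. A test can be run at 0.05 and still be exploratory. On that view the dispute is confined to p-values between 0.0476 and 0.05, and the error moves by a fraction of a percentage point.

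Much of this stands. A reader might infer from the 0.05 sentences that the SAP has abandoned control of OS and ORR claims, and that the error for the pair is 9.75%. The documents do not support that. The gating text is still there, and 9.75% requires both that the gates be ignored and that OS and ORR be independent.

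The reply does not remove the conflict. Section 8.1.2 gives two levels for the same endpoints, and 4.2 gives a testing rule for OS and ORR with no reference to the sequence. The protocol shows a coherent version, but the SAP does not say that the protocol prevails on testing.

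**Conclusion.** The SAP is wrong as written. It states the decision threshold for OS and ORR in two incompatible ways, and only one agrees with the protocol. The result is ambiguity about which rule governs, not a demonstrated loss of error control.

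The consequence depends on the reading. With the gates in force, the excess over 4.76% is small. The approximate doubling shown in step 4 arises only if the gates are set aside. That larger figure rests on an assumed dependence between OS and ORR, and the 5.2% figure rests on an OS or ORR look at the PFS interim that the plan does not describe.

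This should be corrected before the analysis. Protocol 16.4.2 makes the intended rule fairly plain, so the matter is one of consistency and does not call the design into question.

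**What to change.** Change two sentences in the SAP:

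1. In section 4.2, delete the closing 0.05 sentence, or replace it with a reference to the testing procedure in 8.1.2.
2. In section 8.1.2, insert the word *other* in the last sentence, so that 0.05 applies only to secondary endpoints outside the PFS, OS, ORR sequence, in agreement with protocol 16.4.2.

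The protocol needs no change on this point. Sample size, data collection and study conduct are unaffected, and the cost is a minor SAP revision.

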5.0 STUDY DESIGN

This is a multicenter, 1:1 randomized Phase III study of intradermal autologous Vigil immunotherapy (1.0 x 10⁶ cells/injection cells/injection; minimum of 4 to a maximum of 12 administrations) in combination with irinotecan and temozolomide in subjects with metastatic Ewing's sarcoma Family of Tumors (ESFT) refractory/intolerant or recurrent to 1 prior line of chemotherapy. Participants undergoing a standard surgical procedure (e.g., tumor biopsy or palliative resection) may have tumor tissue harvested for manufacture of investigational product.

Subjects meeting eligibility criteria including manufacture of a minimum of 4 immunotherapy doses of Vigil will receive:

Group A

- (i) oral temozolomide 100 mg/m² daily (Days 1 5, total dose 500 mg/m²/cycle),
- (ii) oral irinotecan 50 mg/m² daily (Days 1 5, total dose 250mg/m²/cycle), and
- (iii) Vigil 1.0 x 10⁶ cells/injection, intradermally on Day 15.

OR

Group B

- (i) oral temozolomide 100 mg/m² daily (Days 1 5, total dose 500 mg/m²/cycle), and
- (ii) oral irinotecan 50 mg/m² daily (Days 1 5, total dose 250mg/m²/cycle)

If chemotherapy study drugs cannot be administered orally (i.e. size of capsule, nausea, etc.) it is physician's discretion to request iv administration of temozolomide at 100 mg/m² daily and/or irinotecan 20 mg/m² daily intravenously.

One cycle = 21 days. Screening for the main portion of the study may occur as early as one week but no later than 8 weeks following tumor procurement. Vigil is typically released approximately 3 weeks after the completion of the two-day manufacturing process. At the time of analysis the subjects will be stratified by initial response to frontline treatment (recurrent versus refractory (progressive)).

Participants will be managed in an outpatient setting. Hematologic function, liver enzymes, renal function and electrolytes will be monitored. Blood for immune function analyses including IFNγ-ELISPOT analysis of cytotoxic T cell response to autologous tumor antigens will be collected at tissue procurement, post-procurement screening and prior to chemotherapy administration on Day 1 of Cycles 2, 4, and 6, end of treatment (EOT), 3 months after EOT and every 6 months thereafter. Blood for exploratory ctDNA analysis will be collected at tissue procurement, prior to chemotherapy administration at baseline, prior to chemotherapy administration on Day 1 of Cycles 2, 3, 4, and 6, and EOT.

